6.2 IMPORTANT PROTOCOL VIOLATIONS

A patient's deviation from the trial protocol is considered "important" if it can be expected that the deviation had a distorting influence on the assessment of the treatment effect on the primary endpoint of the trial or could affect the patient's safety or rights.

[Table 6.2: 1](#) gives the important PVs for this trial. The final decision with regard to important PVs and exclusion from the PPS will be made at the final BRPM. Some important PVs will be set automatically; others will need a decision at a Medical Quality Review Meeting (MQRM) or BRPM or through team review of the manual PV log.

In the case that a patient is randomized in both this trial and another trial or is randomized at two different sites in this study the patient will be indicated as having IPV A2 (see [Table 6.2: 1](#)). The following process will be followed with regards to the patient's data.

- All efficacy data will be excluded from the analysis and the patient will be excluded from the Full Analysis Set (FAS) (this trial or both trials as appropriate).
- The only safety data which will be reported is exposure and serious adverse events (SAEs). These will be analysed according to the treatment which the patient actually received. If the patient is randomized twice in this study and both treatments are the same, the patient's data will be combined (i.e., the patient is only counted once). If the patient participates in two different trials in the project, he/she will be reported separately for each trial. As well, care will be taken with regard to the SAE narratives as to whether data for one patient number is relevant for an SAE under the other patient number.
- For disposition, demographics and baseline characteristics the patient will be analysed as treated. If the patient is randomized twice in this study and the treatments are different, the patient will be counted under each treatment. A footnote will be included in the disposition table identifying the situation and noting that the patient is counted twice for disposition as well as baseline data and important protocol violations.

The final decision with regards to important protocol violations and exclusion from the PPS will be made at the final BRPM or database lock meeting before unblinding.

Table 6.2: 1 Important Protocol Violations

Category Code		Description	Requirement	Excluded from
A		Entrance criteria not met		
	A1	Inclusion Criteria not met	Any of inclusion criteria 2 through 6 not met as specified in the protocol.	PPS
	A2	Exclusion Criteria not met	Any of exclusion criteria 2, 3, 9, 12,13, 15, 16, 17, 19, 20, 24, 25 not met as specified in the protocol Any of exclusion criteria 1,4, 5, 6, 7, 8, 10, 11, 12, 14, 18, 21, 22, 23 not met as specified in the protocol	PPS None
B		Informed Consent		
	B1	Informed consent not available /not done	Informed consent date missing; no signature on ICF	All
	B2	Informed consent too late	Date of informed consent was after the date of any study related procedure. If the date of informed consent equals to date of Visit 1, such cases are discussed at MQRM/ BRPM/DBL meetings. Patient signed the wrong version of ICF and then signed correct version with date after randomisation	None
C		Trial medication and randomisation		
	C1	Incorrect trial medication taken	Not throughout study; could be at a clinic visit or between clinic visits	PPS (decision at BRPM)
	C2	Randomisation order not followed and incorrect trial medication taken	Throughout the study, check IVRS	PPS
	C3	Non-compliance with study medication		
	C3.2	Serious non-compliance with study medication as reported in monitoring report	Decision at MQRM/BRPM If at visit 4	PPS
	C4	Medication code broken inappropriately	To be discussed and decided during MQRM/BRPM. Only inappropriate code breaks are IPVs (e.g. unblinding by Global Pharmacovigilance is not).	PPS

Table 6.2: 1 (cont.) Important protocol violations

Category Code	Description	Requirement	Excluded from
D	Concomitant medication		
D1	Improper medication washout at baseline visit or at primary endpoint visits	Visit 2 and Visit 4, refer to Section 4.2.2.2 and Table 4.2.2.1:1 in CTP. Decision at BRPM	PPS
D2	Prohibited medication use during the study	Refer to Table in 4.2.2.1:1 in CTP. Decision at BRPM if in week prior to Visit 2 or Visit 4.	PPS
F	Incorrect timing		
F3	Primary endpoint recorded outside time window		
F.3.1	PFT measurement at 12-hour time point performed more than 13 hours after dosing	Visit 4 Decision at BRPM	PPS
F3.2	PFT measurement at 23:00 or 24:00 planned time performed earlier than 22 hours after dosing at primary endpoint visit(s)	Visit 4 Decision at BRPM	PPS
F4	Trial medication		
F4.1	Trial medication taken prior to pre-dose measurement at baseline visit	Visit 2 Decision at BRPM	PPS
F4.2	Trial medication taken prior to pre-dose measurement at primary endpoint visit(s)	Visit 4 Decision at BRPM	PPS
F4.3	Evening dose of trial medication taken prior to 12h measurements	Visit 4 Decision at BRPM	PPS
F4.4	Drug administration outside time window at randomisation visit and primary endpoint visit.	Visit 2 and Visit 4 start times are both outside 0600 to 1100 inclusive OR (One of Visit 2/Visit 4 start times is outside 6 am to 11 am inclusive AND Visit 2 and 4 morning doses are more than 30 min apart) OR (Visit 4 morning and evening doses do not meet the 12 hours+/- 30 minutes criterion) Decision at BRPM	PPS
Z	Other		
Z1	Serious GCP non-compliance	Manual PVs reported by CML/CRA. Carefully reviewed, described and documented in the DBL meeting minutes Decision at BRPM	PPS
Z2	Other PV affecting efficacy and possible safety	Additional PV identified through monitoring which impacts the primary analysis and possibly patient's rights or safety. Carefully reviewed and documented in BRPM minutes and comment field of IPV ADS.	PPS

Table 6.2: 1 (cont.) Important protocol violations

Z3	Other PV affecting safety only	Additional PV identified through monitoring which impacts patient's rights or safety. Carefully reviewed and documented in BRPM minutes and comment field of IPV ADS.	None
----	--------------------------------	---	------

Note: Missing visits, evaluations, and tests will be considered missing data, not protocol deviations.

IPV categories B2, C1, C2, C3.2, C4, D1, D2, Z1, Z2 and Z3 cannot be checked programmatically and need to be done manually

6.3 PATIENT SETS ANALYZED

There are four patient sets defined in this trial:

- **Randomised Set (RS)**
 This patient set includes all patients who signed the informed consent form and were also randomised, regardless whether the patient was treated with trial medication or not.
- **Treated Set (TS)**
 All randomized patients who were dispensed trial medication and were documented to have taken any dose of trial medication.
- **Full Analysis Set (FAS)**
 This patient set is nested within the TS and includes patients who had baseline and at least one post-baseline measurement for at least one efficacy endpoint. The FAS will be used for the primary analyses of the primary efficacy endpoint and for all other efficacy endpoints.
- **Per Protocol Set (PPS)**
 This patient set is nested within the FAS and only includes patients who had no important PVs which are specified to be excluded from the efficacy analysis. (see [Table 6.2: 1](#)).
- The final decision regarding which patients are included in PPS will be made at BRPM prior to data unblinding.

If the number of patients in PPS is less than 90% of the number of patients in FAS, the primary analysis for the primary endpoint will also be performed on the PPS as supportive analyses.

The analysis will be compliant with ICH guideline [\(5\)](#)

Table 6.3: 1 Patient sets analyzed

Class of endpoint	Treated set	Patient set	
		FAS	PPS
Primary endpoint		primary analysis	*supportive analysis
Key secondary, (other) secondary and further endpoints		X	
Safety	X		
Demographic/baseline	X		

* If the number of patients in PPS is less than 90% of the number of patients in FAS, the primary analysis for the primary endpoint will also be performed on the PPS as supportive analyses.

6.5 POOLING OF CENTRES

This section is not applicable because centre/country is not included in the statistical model.

6.6 HANDLING OF MISSING DATA AND OUTLIERS

Every effort should be made to collect complete data for each time point on each test day.

6.6.1 Spirometry data

The REML-based MMRM model described in Section 7.3.1 will handle missing data due to early drop outs or missing data in between visits which are assumed to be missing at random.

Adjusted multiple imputation will be used to handle missing data in a sensitivity analysis. Details are described in [Section 7.4](#).

FEV₁ and FVC measurements

FEV₁ and FVC measurements at individual time points that are flagged as unacceptable by the vendor will be set to missing prior to applying any missing data imputation rules. Missing FEV₁ and FVC measurements at a given in-clinic visit will be imputed by the available data from the patient at that visit. Completely missing visits will not be imputed and will be handled through the MMRM statistical model expect for cases where a patient discontinues due to an AE indicative of worsening of COPD. For the case of discontinuing due to an AE indicative of worsening of COPD, completely missing visits will be imputed with the worst observation observed before discontinuation.

Discontinuation due to an AE indicative of worsening of COPD will be determined as follows.

- Check that the reason for discontinuation on the termination of trial medication is adverse event.
- Get the AE flagged by the investigator as the primary reason for discontinuation of trial medication.
- Check whether this AE belongs to the group of AEs identified as corresponding to either COPD exacerbation or lower respiratory disorders. This will be based on the BI system in place for grouping MedDRA preferred terms into medical concepts (currently referred to as pharmacovigilance endpoints).

Additional details on the imputation of missing data for specific cases are provided below:

- Any visit occurring more than one day after discontinuation of study medication which has non-missing data will not be used in the analysis.
- For patients taking a short-acting beta agonist (SABA) or short-acting anticholinergic (SAMA) as rescue medication during Visit 3 and 4, any subsequent FEV₁ and FVC measurements from the time of rescue use until time of rescue plus 8 hours (e.g., 2:17 to 10:17) will be set to missing and imputed by the worst non-missing (either observed or imputed) observation for that visit strictly prior to the administration of the rescue medication (even if it is a pre-dose value, either observed or imputed). If there are FEV₁ and FVC measurements after the 8-hour window they will be considered valid and not imputed provided that they are not in the 8-hour window for a subsequent rescue medication use. If rescue medication is taken at any on-treatment in-clinic visit and there is no rescue medication time given, data for the entire visit will be considered missing and it will be handled the same way as the case where all measurements after rescue use are set to missing.
- For randomly missing data (not due to worsening of study disease or rescue medication use), the following rules will be applied:
 - If one of the two pre-dose measurements at Visit 2 is missing, it will be imputed with the other predose measurement.
 - Missing 10 minute pre-dose measurement at Visits 3 and 4 will be imputed with the average of the 23h and 24h post-dose measurements at the same visit if both 23h and 24h time points have non-missing values, or will be imputed with the non-missing measurement at 23h or 24h.
 - If one of the post-dose 23h and 24h measurements is missing at a visit, then impute the missing post-dose measurement with the non-missing one.

- If both of the post-dose 23h and 24h measurements are missing and the 10-min pre-dose measurement is non-missing at a visit, then impute missing 23h and 24h measurements with the non-missing 10-min pre-dose measurement from the same visit.

6.6.2 SGRQ and CAT data

Missing answers for COPD Assessment Test (CAT) and St. George's Respiratory Questionnaire (SGRQ) will be handled based on related manuals [R12-1915R12-2870].

If the baseline SGRQ and CAT is missing the patient will be excluded from all SGRQ and CAT analyses, respectively.

Completely missing visits will not be imputed and will be handled through the MMRM statistical model.

In cases where an entire on-treatment visit is missing after a patient discontinues due to an AE indicative of worsening COPD, all SGRQ component scores and the SGRQ total score as well as CAT score will be imputed using the least favorable prior values for the respective scores.

If SGRQ total score and the CAT score is missing at a visit, the patient will be counted as non-responder for the SGRQ and CAT responder analysis, respectively, at that visit.

6.6.3 Safety data

Missing safety data will not be imputed with the exception of missing AE dates which will be imputed according to BI standards (see Boehringer Ingelheim Data Management and Statistics Manual (DM&SM) "Handling of missing and incomplete AE dates" (2),(3),(4)).

6.7 BASELINE, TIME WINDOWS AND CALCULATED VISITS

The definition of baseline values for FEV₁ can be found in Section 5 of the CTP. The mean of the two pre-dose pulmonary function test measurements at Visit 2, 1 hour prior and 10 minutes prior to the administration of the first dose of the randomised treatment, is used as the baseline FEV₁ and FVC, respectively. For CAT and SGRQ the measurements at Visit 2 is defined as baseline.

Planned and actual study day will be included in the analysis data sets. These will both be calculated relative to the beginning of study as indicated in the following table (nominal visits). See [Table 6.7: 1](#)

Table 6.7: 1 Planned and actual study days

Visit	Planned Study Day	Actual Study Day
2	1	1
3	42	Visit 3 date – Visit 2 date + 1
4	84	Visit 4 date – Visit 3 date + 1
5	105	Visit 5 date – Visit 4 date + 1

7. PLANNED ANALYSIS

For End-of-Text (EoT) tables, the set of summary statistics for descriptive displays is: N / Mean / SD / Min / Median / Max.

Tabulations of frequencies for categorical data will include all possible categories and will display the number of observations in a category as well as the percentage (%) relative to the respective treatment group (unless otherwise specified, all patients in the respective patient set whether they have non-missing values or not). Percentages will be rounded to one decimal place. The category missing will be displayed only if there are actually missing values.

7.1 DEMOGRAPHIC AND OTHER BASELINE CHARACTERISTICS

Only descriptive statistics are planned for this section of the report. COPD background characteristics will be listed only.

GOLD A-D 2017 classifications will be summarized by treatment group.

7.2 CONCOMITANT DISEASES AND MEDICATION

Only descriptive statistics are planned for this section of the report. A table of number (%) of patients with concomitant diagnoses (CDs) by system organ class (SOC) and preferred term (PT) will be included along with a supporting listing. Concomitant diagnoses will be coded with the most recent version of the Medical Dictionary for Regulatory Activities (MedDRA) in effect at database lock.

Frequency tables (%) will be presented for medical history and COPD background characteristics.

Pulmonary medication will be summarized as the number (%) of patients taking pulmonary medications within the last three months before visit 0 and during the treatment periods.

7.3 TREATMENT COMPLIANCE

Only descriptive statistics are planned for this section of the report. Summary statistics will be given for percent compliance along with the number (%) of patients with compliance in the categories <80% or >120%, 80% - 120%.

7.4 PRIMARY ENDPOINT

In the primary analyses, comparisons between treatment groups for the primary endpoint will be based on a mixed effects model repeated measures (MMRM). Change from baseline in FEV₁ AUC_{0-24h}, will be analysed using a restricted maximum likelihood (REML)-based repeated measures approach. This model will include treatment, visit and treatment by visit interaction as fixed effects, and baseline as well as baseline by visit interaction as covariates. An unstructured covariance structure will be used to model the within patient errors. The SAS procedure MIXED will be used for the restricted maximum likelihood estimation and Kenward-Roger approximation for denominator degrees of freedom. Adjusted mean values as well as treatment contrasts will be presented together with 95% confidence intervals. The primary treatment comparisons will be the contrasts between treatments after 12 weeks of treatment.

```
PROC MIXED DATA=alldat cl method=reml order=formatted;  
CLASS usubjid ptrsort tptno;  
MODEL ept = ptrsort*tptno eptbase*tptno  
/ ddfm=kr solution;  
REPEATED tptno / subject=usubjid type=un r rcorr;  
LSMEANS tptno*ptrsort / pdiff=all om cl alpha=0.05 slice=tptno;  
RUN;
```

Here tptno is the planned analysis day number for each visit. The endpoint is ept, baseline value of the endpoint is eptbase, treatment is ptrsort and patient number is usubjid.

In the event of non-convergence, the following methods will be attempted (in order) to overcome it:

1. Add the 'singular=1e-10' option in the model statement – This raises the threshold at which columns are declared linearly dependent (from typically 1e-12).
2. Set 'maxiter=100' in the Proc Mixed statement – This increases the number of convergence iterations used from a default of 50.
3. Set 'scoring=4' to specify use of the Fisher scoring algorithm in the first 4 iterations.
4. Include the statement 'performance nothread' – this removes multi-threading from the calculations.

If the number of patients in PPS is less than 90% of the number of patients in FAS, then the primary analyses for the primary efficacy endpoints will be repeated using PPS and the results will be presented as supportive analyses

7.4.1 Adjusted Multiple Imputation sensitivity analysis for missing data

The MMRM primary analysis implicitly accounts for missing observations under the MAR (missing at random) assumption. The robustness of the primary analysis to the MNAR (missing not at random) assumption will be assessed by performing an adjusted multiple imputation sensitivity analysis.

The aim of the multiple imputation approach is to assess the robustness of the primary analysis with respect to departures from MAR by applying specific shift parameters to missing data in the T+O 5/5 arm, corresponding to substantially worse outcomes for these patients.

As a first step non-monotone missing data will be imputed $m = 100$ times using MCMC (Markov Chain Monte Carlo) under an assumption of MAR to generate m data sets with monotone missingness. This large number of imputations is chosen to minimize the standard error of the estimates. The seed number will be set to 123763.

The monotone missing data in the 100 generated datasets will then be imputed once per each of the 100 imputations using sequential regression including baseline FEV₁ and Week 6 FEV₁ AUC_{0-24h} as covariates in the model, with a shift parameters S applied to the treatment arm T+O 5/5 at the first missing visit and no shift applied to the F+S 250/50 treatment arm. Subsequent visits will have no additional shift but due to the sequential method, the impact of the initial shift will propagate to all future visits.

Point estimates for treatment differences and respective p-values will be reported for all S .
Selection of S

- a. -250 ml (large shift, conservative analysis)
- b. -125 ml,
- c. negative treatment difference from the primary analysis

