7.2 NULL AND ALTERNATIVE HYPOTHESES

The following primary hypothesis will be tested at 5% level of significance (two-sided):

H_0 : Mean FEV₁ AUC_{0-24h} response (change from baseline) [L] after 12 weeks of treatment for tiotropium (LAMA) +olodaterol (LABA) (5µg/5µg) = Mean FEV₁ AUC_{0-24h} response (change from baseline) [L] after 12 weeks of treatment for fluticasone propionate(LABA) +salmeterol (ICS) (250µg/50µg)

H_1 : Mean FEV₁ AUC_{0-24h} response (change from baseline) [L] after 12 weeks of treatment for tiotropium (LAMA) +olodaterol (LABA) (5µg/5µg) \neq Mean FEV₁ AUC_{0-24h} response (change from baseline) [L] after 12 weeks of treatment for fluticasone propionate(LABA) +salmeterol (ICS) (250µg/50µg)

The secondary analyses will be performed using the same methodology as the primary analysis.

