7.7 DETERMINATION OF SAMPLE SIZE

Calculations were performed using nQuery Advisor[®] 6.1 statistical package by Statistical Solutions Ltd.

Assuming a standard deviation of 0.22L a total sample size of 274 completed patients, will be able to detect a treatment difference of .075 L, for FEV₁ AUC_{0-24h} with 80% power, using a two-sided test at $\alpha=0.05$ for superiority testing. The assumptions for sample size calculation are based on the results of 1237.5, 1237.6, and 1237.11 studies. Assuming a maximum 5% drop-out rate, in order to ensure that 274 completers, 288 patients will be randomized.

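### Does the shift analysis in SAP 7.4.1 start from the wrong place because its imputation model names no treatment term and no zero shift is listed?

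*SAP*

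**What the plan says.** SAP 7.4.1 imputes in two steps. Non-monotone gaps are filled 100 times by MCMC "under an assumption of MAR to generate m data sets with monotone missingness"; no variables are listed for this step. The remaining monotone gaps are then "imputed once per each of the 100 imputations using sequential regression including baseline" FEV1 and Week 6 FEV1 AUC0-24h. The arm is mentioned only where the shift S is applied: to T+O 5/5 "at the first missing visit and no shift applied to the F+S 250/50 treatment arm". S takes three values: -250 mL, -125 mL, and minus the treatment difference from the primary analysis. "Point estimates for treatment differences and respective p-values will be reported for all" values of S.

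The model under test is the MMRM of SAP 7.4: "This model will include treatment, visit and treatment by visit interaction as fixed effects". SAP 7.4.1 opens by saying that this model handles missing data under MAR.

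Two other passages bear on how much is imputed. For a discontinuation caused by an adverse event indicating worsening COPD, SAP 6.6.1 says that "completely missing visits will be imputed with the worst observation observed before discontinuation". Protocol 7.7 sets the planning rate: "Assuming a maximum 5% drop-out rate".

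**The concern.** A shift analysis is easiest to read when S = 0 reproduces the MAR result, so that all movement away from it is due to S. If the imputation model leaves out treatment while the analysis model contains it, imputed values in both arms are drawn towards a common mean. A patient missing both visits then contributes no treatment difference. A patient missing only Week 12 keeps most of it, because the observed Week 6 value carries it.

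The estimate at each S would then combine the intended shift with an unplanned pull towards no difference. With no S = 0 result in the output, a reader could not separate the two. What is at stake is how the smaller shifts are read, not the primary test.

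**Working it through.** **Inputs from the documents.** Difference 75 mL, SD 220 mL, 274 completers, 288 randomised and 5% maximum drop-out (Protocol 7.7); two-sided 5% test (Protocol 7.2); 1:1 allocation (Protocol 4.1.3).

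**Assumptions, not in the documents.** The 75 mL difference holds at both visits; the Week 6 to Week 12 correlation ρ is 0.5 to 0.9; loss is non-informative and equal in the two arms; a share q of the missing patients lacks both visits, with q anywhere from 0 to 1.

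**The plan's own figure.** A two-sample t calculation with 75 mL, SD 220 mL and two-sided 0.05 gives 137 per arm, 274 in total, with power 80.3%. This matches Protocol 7.7. Inflating by 5%, 274 × 1.05 = 287.7, which rounds up to the stated 288. The standard error of the difference is 220 × √(2/137) = 26.6 mL.

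**Literal reading: no treatment term, S = 0.** The pooled slope of Week 12 on Week 6 is

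b = (ρ × 220² + 75²/4) / (220² + 75²/4) = (ρ × 48,400 + 1,406.25) / 49,806.25,

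which gives 0.514, 0.806 and 0.903 for ρ = 0.5, 0.8 and 0.9.

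Patients missing only Week 12 contribute b × 75 mL instead of 75 mL. Patients missing both visits contribute 0. With missing share m, the loss in the estimate is

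m × 75 × [q + (1 − q)(1 − b)].

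For m = 0.05, m × 75 = 3.75 mL, and the loss in mL is:

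| Pattern | ρ = 0.5 | ρ = 0.8 | ρ = 0.9 |
|---|---|---|---|
| All miss Week 12 only (q = 0) | 1.82 | 0.73 | 0.36 |
| Half miss both visits (q = 0.5) | 2.79 | 2.24 | 2.06 |
| All miss both visits (q = 1) | 3.75 | 3.75 | 3.75 |

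The S = 0 estimate would therefore lie between 75 − 3.75 = 71.25 mL and 75 − 0.36 = 74.64 mL. The largest loss is 3.75 / 26.6 = 0.14 SE. As a rough guide, the ratio of estimate to standard error goes from 75 / 26.6 = 2.82 to 71.25 / 26.6 = 2.68.

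**Simulation check.** With 144 per arm, ρ = 0.8, 5% missing, 1,500 trials and 10 imputations, the result without treatment minus the result with treatment at S = 0 was −0.70, −2.34 and −3.79 mL for q = 0, 0.5 and 1. The formula gives −0.73, −2.24 and −3.75. The Monte Carlo standard error was at most 0.08 mL. At S = −250 mL the gaps were −0.71, −2.31 and −3.92 mL, so the offset hardly depends on S.

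**Sensible reading: treatment included.** In a separate simulation with treatment in the regression, the S = 0 estimate agreed with the MAR likelihood estimate to within about 0.2 mL.

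**Comparison with the planned shifts.** If the missing patients lack Week 12 only, S moves the estimate by 0.05 × S: 6.25 mL for −125 and 12.5 mL for −250. For the third choice, at a primary estimate of 75 mL, it moves by 3.75 mL.

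**The case for a change.** The best argument for a change is that this detail belongs in the SAP. Protocol 7.3.2 leaves the missing-data sensitivity analyses to it, and SAP 7.4.1 goes as far as fixing the seed and the number of imputations. Two programmers could still read the covariate list differently. The third shift also has a natural meaning, no benefit in missing patients, only if treatment is in the model. With ρ = 0.8 and the literal reading, patients missing only Week 12 would have an imputed difference of (0.806 − 1) × 75, about −15 mL, instead of zero. Patients missing both visits can occur in the analysis, because the FAS of SAP 6.3 requires a post-baseline value for only one efficacy endpoint.

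The first part stands: the text leaves the imputation model open. But an open list is not a wrong rule. The list cannot be exhaustive for every visit, since Week 6 cannot be a covariate for itself, and the section's MAR basis points to a model containing treatment. The point about the third shift is right per patient, but those patients carry a weight of 5% or less, which is the 0.73 mL in the table.

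The share imputed here may also be below 5%. COPD-worsening discontinuations are filled by the separate rule in SAP 6.6.1, and partly missing visits are filled within the visit. Finally, the MCMC step fills a missing Week 6 value when Week 12 is observed, so it has little bearing on the Week 12 contrast.

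**Conclusion.** No change to the plan is needed. This is a gap that an analyst fills sensibly: a program that imputes under the MAR assumption of a model with treatment by visit will carry treatment or run by arm, and S = 0 then reproduces the MAR estimate.

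If the two named covariates were used alone, the estimates would be about 0.4 to 3.75 mL too low at 5% missing, at most 0.14 SE. Whenever T+O is the better arm, the pull goes against T+O, so it makes a deliberately conservative analysis slightly more so and cannot produce false robustness. The primary analysis is unaffected. The MMRM already supplies the MAR reference, so listing S = 0 would add only a check on the programming.

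The size rests on a 75 mL difference at both visits, equal non-informative loss, and a correlation of 0.5 to 0.9. Under equal loss the ceiling, missing share times difference, holds for any non-negative correlation and any mix of missing patterns. It rises in proportion if more than 5% are missing.
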